250422. Analysis plan: Twin threat of OSA and hypertension on mortality and protective effect by positive airway pressure treatment. ClinicalTrials.gov Identifier: NCT06930989

250422 Gothenburg, Sweden

Analysis plan: Twin threat of OSA and hypertension on mortality and protective effect by positive airway pressure treatment.

ClinicalTrials.gov Identifier: NCT06930989

[name]

[contact]

[name]

Analysis plan: Twin threat of OSA and hypertension on mortality/CV-risk and protective effect by positive airway pressure treatment.

HYPOTHESIS

1. Patients with hypertension and obstructive sleep apnea (OSA) have increased risk of MACE (major cardiovascular events and death from these events; stroke, cardiovascular death, acute myocardial infarction, incident heart ischemia or heart failure) or premature death of any cause compared to HT alone or OSA alone and compared to healthy controls.
2. OSA patients compliant with PAP have reduced OSA related risk.

STUDY DESIGN

Discovery[1] (“Course of DISease in patients reported to the Swedish CPAP Oxygen and VEntilator RegistrY”) 2.0 is a large clinical cohort on patients with home mechanical ventilation, long-term oxygen treatment and/or CPAP treatment with data from the Swedish national register for patients on Long Term Oxygen Therapy and Home Mechanical Ventilation (Swedevox) and the Swedish Sleep Apnea Registry (SESAR). Data are cross referenced using Swedish personal IDs with data from multiple Swedish national registries including the National Patients diagnosis registry, National prescription registry, National Cause of Death Register, and SCBs registries on socioeconomic information. Data quality in the SWEDEVOX and SESAR registries have been validated for accuracy[2].

The following *inclusion criteria* will be applied:

- All adult patients that started PAP treatment during 2010-2021 in Swedevox with diagnosis of OSA with or without comorbid hypertension diagnosis within 5 years prior

initiation of CPAP therapy.

- Randomly selected individuals from the general population without a known OSA diagnosis but with and without arterial hypertension are selected for control groups.

Exclusion criteria for study participation are:

- Patients with manifest cardiovascular disease (stroke, ischemic heart disease, cardiac failure or atrial fibrillation at baseline).
- Patients with kidney failure at baseline.
- Patients with malignant cancer at baseline.

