The study protocol was approved by the Ethics Committee at the Medical Faculty at Lund University and the Swedish Ethical Review Authority, Dnr. 2018/51, 2019/01420, 2020/02721, 2021/04984, 2022-00745-02, 2022-02012-02, 2022-05523-02, 2024-05277-02, and 2025-00712-02. According to Swedish law, patients entering a national quality registry like Swedevox are informed, can withdraw from registration at any time, but do not sign an informed consent.

Statistical analyses

Continuous data following a normal distribution will be reported as mean \pm standard deviation (SD), while data with a skewed distribution will be presented as median along with the interquartile range (IQR). Categorical data will be represented as frequencies and percentages. Categorical variables will be

analyzed with the chi-squared test, normally and non-normally distributed continuous variables will be analyzed with Student's t-test and the Wilcoxon rank-sum test respectively. ANOVA is used to compare variables between groups.

Medians and 95% CI are reported for follow-up time for the groups and total.

Mortality and MACE incidence will be visualized using Kaplan-Meier cumulative mortality/incidence estimate curves. Survival differences between groups will be analyzed using log-rank tests. Crude and adjusted Cox proportional survival analyses will be made. Covariates are selected using current literature, clinical experience and directed acyclic graphs. Hazard Ratio, Relative Risk, and CI are reported for COX analyses. Separate Cox proportional survival analyses will be made to investigate difference between the two OSA groups and to assess PAP protective effect and adherence in a similar manner.

Both all-cause death and MACE/CV related deaths will be reported separately for primary and secondary outcomes.

All estimates will be presented with 95% confidence intervals (CIs). Statistical significance is defined as a two-sided p-value < 0.05.

DATA MANAGEMENT

Definition of primary outcome

Hazard ratios for all groups MACE/death event risk. Mean age at MACE/death event for all groups.

Definition of secondary outcome

[figure not shown]
Modifying effect of PAP treatment analysis stratified by compliance/daily usage time per night on primary outcomes.

Definition of exposure

Hypertension diagnosis and or OSA for primary outcomes.

PAP treatment (Swedevox 2010-2023) for secondary outcomes.

DAG:

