Lifestyle factors include smoking, food habits and physical activity, where we lack data. Will be indirectly controlled for thru inclusion of socioeconomic factors, anthropometrics, compliance of treatments and obstructive lung disease.

Analysis plan: The synergistic effect of OSA and hypertension on mortality can be attenuated by positive airway pressure treatment.

Variables and timing of variables to be obtained from database(s):

Below are the variables to be considered in the analysis listed.

All non-outcome variables for baseline inclusion as well as latest available at study end. For sleep data first available data will be considered baseline information.

Sleep data

AHI, ODI, ESS (Epworth sleepiness scale), mean saturation. Date of OSA diagnosis and PAP start.

Baseline or if missing; above mentioned data are possibly available from the CPAP start. For sleep data first available data will be considered baseline information.

Sleep follow-up data during treatment follow-up

PAP compliance (hrs/day) closest before MACE/death or end of study. Continuous and stratified compliance and considered to have the same compliance for rest of study duration.

ESS.

Medication

All **AHT before PAP start, last year before MACE/death or study end.** Patients picking up a drug at least twice during the last year are considered on that drug for a visit. *Dosing needed separately for each drug.*

Statins at baseline and end of study.

Number of medication pickup dates for each calendar year will be calculated and used for compliance estimations.

Diagnosis

All diagnoses before PAP start and end of study. MACE or new AF *at any time.* Reasons for death when applicable.

ICD codes of interest (both patient registries and/or swedevox):

Diabetes (E10-E14), Hyperlipidemia E78, COPD J44, Kidney failure (N17-N19), Depression F32 and 33, Hypertension (I10-I15), OSA G47.3, ischemic heart disease (I20-25), AF I48, Cardiac failure I50, Stroke I61-66. Malignant cancer C00-C97. Ischemic heart disease or infarction, Atrial fibrillation, Cardiac failure or Stroke *Baseline and first new diagnosis for MACE.*

All else *baseline and study end.*

Socioeconomic data

Baseline and study end. European socioeconomic classification (ESeC/YSEG in SCB), Education level, Income quartiles.

Smoking

Indirectly assessed through “Obstructive lung disease” (diagnosis captured from medication use), socioeconomic variables, BMI and compliance with primary preventive treatments.

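### The SAP is inconsistent on whether a new non-fatal atrial fibrillation diagnosis counts as a MACE event

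*SAP*

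**What the plan says.** Four places in the SAP bear on the point.

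- **Hypothesis 1** gives the only worded definition of MACE: "stroke, cardiovascular death, acute myocardial infarction, incident heart ischemia or heart failure". AF is not in it.
- **Diagnosis, opening lines**, asks for "MACE or new AF *at any time". This puts new AF next to MACE, not inside it.
- **Diagnosis, ICD codes of interest**, gives I48 for AF and then states "Ischemic heart disease or infarction, Atrial fibrillation, Cardiac failure or Stroke *Baseline and first new diagnosis for MACE". The remaining conditions follow under a different rule: "All else *baseline and study end".
- **Death registry** includes I48 among the codes for cardiovascular death, so fatal AF enters MACE by that route.

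The exclusion criteria remove "Patients with manifest cardiovascular disease (stroke, ischemic heart disease, cardiac failure or atrial fibrillation at baseline". The primary outcome is the hazard ratio for MACE/death together with "Mean age at MACE/death event for all groups", and the Outcomes list censors patients after their first event. The later sections use MACE without defining it again.

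**The concern.** The ICD paragraph is where a programmer finds the codes for deriving non-fatal events. It gives AF the same role as three true components of the composite and says that the first new diagnosis is taken for MACE. Followed literally, it adds a component that the stated definition does not contain.

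Because AF at baseline is an exclusion, every AF diagnosis in follow-up is a new one, and this wording alone decides whether it is an event. Because follow-up for the outcome stops at the first event, the rule sets event dates as well as counts. It therefore reaches the MACE hazard ratio, the mean age at event, and the secondary analyses of MACE by PAP use. If the matter is left open, the composite could also be settled after the data have been seen.

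**Working it through.** **Text check.** The SAP states no event rate, event count or power figure on this point, so there is no figure of the plan's own to reproduce. The check is whether any passage settles the status of non-fatal AF.

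1. Hypothesis 1 keeps it out, by omission from a closed list.
2. The opening of Diagnosis keeps it out, by naming it as an alternative to MACE.
3. The ICD paragraph puts it in, by listing it among the diagnoses read for MACE.
4. The Death registry codes cover fatal AF only and say nothing about a non-fatal diagnosis.
5. The baseline exclusion explains why AF must be read at baseline. It does not explain why a first new diagnosis is read for MACE.

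Two places leave non-fatal AF out, one puts it in, and none resolves the conflict.

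**Illustrative size.** Every input here is an assumption; none comes from the SAP.

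- Reference hazard of the other MACE components: 1.2% per year; hazard ratio 1.20 in the exposed group.
- Non-cardiovascular death: 0.8% per year in both groups.
- AF hazard in the reference group: f × 1.2% per year, with f = 0.1, 0.2 or 0.4.
- AF hazard ratio h = 1.0, 1.2, 1.4 or 1.6.
- MACE hazard multiplied by k = 1, 2 or 4 after AF.
- Two equal groups, constant hazards, 10 years of follow-up for all.

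With AF counted, the first-event hazard ratio is (1.2 + f·h)/(1 + f). Two examples:

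- f = 0.4, h = 1.0: 1.6/1.4 = 1.143
- f = 0.4, h = 1.6: 1.84/1.4 = 1.314

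With AF not counted, the ratio is exactly 1.20 when k = 1. For k above 1 it is the large-sample Cox limit, solved numerically.

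| AF hazard ratio h | MACE HR, AF counted | MACE HR, AF not counted | Difference within a scenario |
|---|---|---|---|
| 1.0 | 1.143 to 1.182 | 1.199 to 1.200 | −0.057 to −0.018 |
| 1.2 | 1.200 | 1.200 to 1.212 | −0.012 to 0.000 |
| 1.4 | 1.218 to 1.257 | 1.200 to 1.225 | +0.011 to +0.057 |
| 1.6 | 1.236 to 1.314 | 1.200 to 1.238 | +0.026 to +0.114 |

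The two outer values arise at f = 0.4 and k = 1: 1.143 − 1.200 = −0.057 and 1.314 − 1.200 = +0.114. At k = 1 they depend on neither the base rates nor the length of follow-up.

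The ratio of patients with an event, AF counted to not counted, runs from 1.069 (f = 0.1, k = 4, h = 1.0) to 1.428 (f = 0.4, k = 1, h = 1.6), an increase of about 7–43%. The square roots, 1.034 and 1.195, mean that the standard error of the log hazard ratio is about 3–20% larger when AF is not counted.

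**The case against.** The strongest reply is that the ICD line is not a second definition. It stands under a heading about variables and their timing, and its italics give read times. On that reading AF shares the row only because it is needed for the exclusion and as new AF, and the closing reference to MACE is loose. This has weight: the definition and the opening of the section agree with each other, so the intended rule is probably to leave AF out. But the opening lines already fix when new AF is collected. What the ICD line adds is the purpose, and a timing reading does not account for that.

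The reply is also right that the size rests on chosen inputs. The widest differences need the largest AF share together with the lowest or highest AF hazard ratio, and the rise in events largely restates the assumed share.

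Three stronger readings are tempting, and the SAP does not support them.

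- **A quantified shift in the PAP reading.** Since the SAP takes "PAP compliance (hrs/day) closest before MACE/death or end of study", a reader might infer that counting AF moves that reading by a calculable number of years. PAP starts run from 2010 to 2021 and follow-up ends in October 2022, so possible follow-up runs from about 0.8 to 12.8 years, and no single length fits. Controls have no PAP data. An earlier reading date matters only if another, different reading lies in between, and the SAP does not show that.
- **A shift in the antihypertensive covariates.** The Medication section reads "AHT before PAP start, last year before MACE/death or study end", which might suggest that these move too. The listed covariates are the number of drugs at baseline and compliance, which is defined over individual study time. None is expressly the last-year reading.
- **An effect on every primary result.** All-cause death is analysed and reported separately, and its events do not depend on AF.

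**Conclusion.** The inconsistency is real and no passage resolves it. It is confined to non-fatal AF and to MACE: the event count, first-event date, hazard ratio, mean age at MACE, and the PAP analyses of MACE.

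Neither the size nor the direction can be derived from the SAP. Under the assumptions shown, counting AF changes the MACE hazard ratio by about −0.06 to +0.11 and raises the number of patients with an event by about 7–43%. If AF has the same hazard ratio as the other components, the hazard ratio hardly moves. The mean age at event shifts only if AF occurs at a different age from the other events.

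This should be corrected before analysis because it alters a primary composite. It does not show that the sponsor intends to count AF, or that any result would be biased in a given direction.

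**What to change.** Apply the Hypothesis 1 definition throughout and replace the one line in the ICD paragraph, for example with:

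*Non-fatal MACE is the first new diagnosis of ischemic heart disease or infarction (I20–I25), cardiac failure (I50) or stroke (I61–I66); each is also read at baseline. AF (I48) is read at baseline for the exclusion and at its first new diagnosis, and is not counted as non-fatal MACE.*

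Leave the cardiovascular-death codes as they are, so that fatal AF still counts through cardiovascular death. State that new AF, if reported at all, is reported descriptively; no new outcome is needed.

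The change is to wording only, since the SAP already collects these diagnoses from the registers. The downside is fewer MACE events and somewhat wider intervals if AF was being counted, with a standard error of the log hazard ratio about 3–20% larger under the same assumptions.
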